4.8.3 Efficacy

4.8.3.1 Primary Efficacy Analysis

The primary objective of this study is to evaluate the effect of 3 dose levels of MEDI9929 on asthma exacerbations in adult subjects with inadequately controlled, severe asthma. The primary endpoint is a reduction in the annualized asthma exacerbation rate (defined in Section 4.3.1) measured at Week 52.

The annual AER will be presented as a weighted mean (total number of exacerbations for the treatment group divided by the total duration of person follow-up) per the joint guidelines recommended by the ATS/ERS. The primary endpoint analysis will be conducted using a negative binomial regression model with treatment group, baseline blood eosinophil count (≥ or < 250 cells/µL), and baseline ICS dose level (medium or high) as covariates. Because the treatment effect in the non-Japanese population is not expected to be different from the Japanese population, the stratification factor of study sites (non-Japanese or Japanese) will not be included as a covariate for the primary analysis. The follow-up time will be adjusted by offset option. The primary comparisons are as follows: MEDI9929 280 mg Q2W versus placebo; MEDI9929 210 mg Q4W versus placebo; and MEDI9929 70 mg Q4W versus placebo.

As a sensitivity analysis, the annual AER may be assessed by a Poisson regression model to assess the robustness with regard to the distributional assumptions. In a Poisson regression model, the correction for potential over-dispersion will be made by Pearson chi-square method. The same covariates used for the negative binomial regression model will be considered.

The primary analysis will be conducted based on the ITT population. As sensitivity and supportive analyses, the primary analysis may be repeated based on the PP population.

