4.3.4 Clinical Laboratory Tests

A Laboratory Manual will be provided to the sites that specifies the procedures for collection, processing, storage, and shipment of samples, as well as laboratory contact information, specific to this clinical research study.

Clinical laboratory safety tests including serum pregnancy tests will be performed in a central clinical laboratory. In addition to the safety laboratory hematology samples at the central clinical laboratory, a complete blood count with differentials will be performed at the site's local laboratory at Visit 1 (Week -5) and Visit 3 (Week -1). The Visit 3 (Week -1) blood eosinophil count from the local laboratory will be used for stratification.

Urine pregnancy tests may be performed at the site using a licensed test (dipstick). Abnormal laboratory results should be repeated as soon as possible (preferably within 24 to 48 hours).

The following clinical laboratory tests will be performed (see Table 4.2.1-1, Table 4.2.2-1, Table 4.2.2-2, Table 4.2.3-1 for the schedule of tests):

Serum Chemistry

- Calcium
- Chloride
- Potassium
- Sodium
- Bicarbonate
- Aspartate transaminase (AST)
- Alanine transaminase (ALT)
- Albumin

- Uric acid
- Creatinine
- Total bilirubin
- Glucose
- Alkaline phosphatase (ALP)
- Blood urea nitrogen (BUN)
- Total protein

Note for serum chemistries: Tests for AST, ALT, ALP, and total bilirubin must be conducted concurrently and assessed concurrently. In the event that the AST or ALT is elevated $\geq 3 \times \text{ULN}$, creatine kinase will be measured.

Hematology

- White blood cell (WBC) count with differential Platelet count
- Red blood cell (RBC) count
- Hematocrit
- · Hemoglobin

Urinalysis

- Nitrites (dipstick)
- Protein (dipstick)
- Glucose (dipstick)
- Ketones (dipstick)

- Blood (dipstick)
- Bilirubin (dipstick)
- Urine microscopy and urine casts (as required)
- Urine culture (as required)

Pregnancy Test

Serum beta-hCG (at screening only, required of all females)

Urine human chorionic gonadotropin (hCG, required for females of childbearing potential only)

Other Safety Tests

- Hepatitis B surface antigen, hepatitis C antibody (screening only)
- HIV-1 and HIV-2 antibody (screening only)

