4.6 Treatment Assignment and Blinding

4.6.1 Methods for Assigning Treatment Groups

An IXRS will be used for randomization to a treatment group and assignment of blinded investigational product kit numbers.

A subject is considered randomized into the study when the investigator or designee notifies the IXRS that the subject meets eligibility criteria and the IXRS provides the assignment of blinded investigational product kit numbers to the subject.

Prior to randomization, subjects will be stratified by study site (non-Japanese and Japanese), then subjects will be stratified by blood eosinophil count (\geq or < 250 cells/ μ L) and by ICS dose level (medium or high). Subjects taking maintenance OCS will be automatically assigned to the high-dose ICS strata. There will be a total of 8 strata; 4 strata for non-Japanese subjects and 4 identical strata for Japanese subjects (see Section 3.1.1 for strata descriptions).

Subjects will then be randomized at a 1:1:1:1 ratio to receive either MEDI9929 (280 mg [Q2W], 210 mg [Q4W], or 70 mg [Q4W]) or placebo.

Investigational product (MEDI9929 or placebo) must be administered the same day the investigational product is assigned. If there is a delay in the administration of investigational product such that it will not be administered within the specified timeframe, the study monitor must be notified *immediately*.

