4.8 Statistical Evaluation

4.8.1 General Considerations

Data will be provided in data listings sorted by treatment group and subject number. Tabular summaries will be presented by treatment group. Categorical data will be summarized by the

number and percentage of subjects in each category. Continuous variables will be summarized by descriptive statistics, including mean, standard deviation, median, minimum, and maximum. Confidence intervals (CIs) will be two-sided and all efficacy analyses will be conducted with a two-sided test at the 0.1 significance level, unless otherwise stated. Baseline value will be defined as the last valid assessment prior to the first administration of investigational product on Day 1.

No missing data will be imputed for the primary endpoint. Missing data imputation methods for the secondary endpoints will be specified in the statistical analysis plan (SAP). The primary endpoint will be tested using a stepdown method for 3 hypotheses (from the high dose [280 mg Q2W] to the medium dose [210 mg Q4W] to the low dose [70 mg Q4W] when compared with placebo) to maintain the overall type-1 error rate at 0.1 (two sided). Nominal p-values will be provided for the selected secondary efficacy endpoints (pulmonary function, ACQ-6, AQLQ(S)+12, and Asthma Daily Diary) without multiplicity adjustment.

For the selected secondary efficacy endpoints that are continuous variables, a generalized linear mixed model using a linear contrast test including treatment group, visit, treatment-by-visit interaction, baseline blood eosinophil count (≥ or < 250 cells/µL), baseline ICS dose level (medium or high), and the respective baseline measure for the given endpoint as fixed effects may be used to compare the change from baseline at Week 52 for each efficacy endpoint between the individual MEDI9929 dose groups and the placebo group, respectively. No p-values will be reported for other PROs. Additional details of statistical analyses will be described in the SAP.

The intent-to-treat (ITT) population is defined as all subjects who are randomized and receive any investigational product. Treatment group will be assigned according to the initial randomization, regardless of whether subjects receive an investigational product different from that to which they were randomized. This is the primary efficacy population.

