4.8.2 Sample Size and Power Calculations

Sample size calculations have been performed for the primary endpoint of annualized AER, based on the negative binomial distribution (Keene et al, 2007). Approximately 552 subjects will be randomized in the study, with approximately 85% of the total number of subjects designated as non-Japanese subjects (ie, subjects enrolled at sites outside of Japan) and approximately 15% of the total number of subjects designated as Japanese subjects (ie, subjects enrolled at sites in Japan). The total enrollment may exceed 552 subjects depending on whether additional non-Japanese subjects are enrolled to mitigate for slow enrollment in Japan, and to accommodate subjects in screening/run-in when the different strata are closed to enrollment.

Subjects will be randomized in a 1:1:1:1 ratio to receive one of 3 dose levels of SC MEDI9929 (280 mg Q2W, 210 mg Q4W, or 70 mg Q4W) or placebo Q2W for 52 weeks. Prior to randomization, subjects will be stratified by study site (non-Japanese and Japanese) and then by blood eosinophil count (\geq or< 250 cells/ μ L) and ICS dose level (medium or high). Subjects taking maintenance OCS will be automatically assigned to the high-dose ICS strata. At least 50% of the total subjects will be enrolled in the high blood eosinophil stratum (\geq 250 cells/ μ L), and at least 40% of the subjects in each blood eosinophil stratum will be receiving high-dose ICS. Details on the 8 strata (4 strata for non-Japanese subjects and 4 identical strata for Japanese subjects) are included in Section 3.1.1.

The primary analysis will be based on the ITT population. The 3 primary comparisons are as follows: MEDI9929 280 mg Q2W versus placebo; MEDI9929 210 mg Q4W versus placebo; and MEDI9929 70 mg Q4W versus placebo. A total of 124 subjects per treatment group would be required to detect a 40% reduction in the annual AER for each MEDI9929 dose group compared to placebo group, assuming an AER of 0.7 in the placebo group, a two-sided significance level of 0.1, 80% power, and a dispersion parameter of 0.7 based on the negative binomial distribution. The AER of 0.7 in the placebo group was estimated based on internal and external studies with a similar subject population (before considering dropouts). The dispersion parameter of 0.7 was selected from the mepolizumab study in subjects with severe, eosinophilic asthma (Pavord et al. 2012). Sample size was increased to 138 per

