4.8.3.2 Secondary Efficacy Analyses

Efficacy Outcomes in Pre-specified Subpopulations of Asthma

The primary endpoint of a reduction in the annualized AER measured at Week 52 and two other secondary endpoints of change from baseline in FEV_1 and in overall symptom score at Week 52 will be analyzed by the following pre-specified subpopulations of asthma:

1) eosinophilic and non-eosinophilic; 2) Th2 high/low (Corren et al, 2011); 3) FE_{NO} high/low; 4) periostin high/low; 5) current post-BD FEV₁ reversibility; and 6) allergic and non-allergic asthma.

Pulmonary Function

The effect of MEDI9929 on pulmonary function as measured by pre- and post-BD FEV_1 and FVC at the site, and PEFR at home will be assessed during the study. Change from baseline in the mean values and percent change from baseline at various time points will be summarized using descriptive statistics. Change from baseline in the mean values and percent change from baseline of FEV_1 and FVC at Week 52 will be analyzed.

Additional Analyses of Asthma Exacerbation

The analysis of exacerbations will also be conducted specifically for severe asthma exacerbations (hospitalizations). In addition, asthma exacerbations and severe asthma exacerbations through Week 64 will also be summarized.

Time to first asthma exacerbation and time to first severe asthma exacerbation will be analyzed as a supportive efficacy analysis for the primary objective using a log-rank test. Incidence of asthma exacerbations will also be evaluated by the proportion of subjects having one or more asthma exacerbations and one or more severe asthma exacerbations during the study.

Optimal Dose and Regimen

Dose response may be evaluated based on quadratic and linear negative binomial regression models to detect the dose response. The E_{max} model may be generated to determine the minimum effective dose. The details of the dose response analysis will be described in the SAP.

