4.8.4 Patient-reported Outcomes

Asthma Control Questionnaire-6

Asthma control will be evaluated by ACQ-6. The change from baseline in the mean ACQ-6 score will be analyzed. The proportion of subjects with change from baseline in the mean ACQ-6 score ≥ 0.5 during the study and the proportion of subjects who are well controlled (mean ACQ-6 score of ≤ 0.75), partially controlled (0.75 < mean ACQ-6 score ≤ 1.5), and uncontrolled (mean ACQ-6 score ≥ 1.5) will be compared between the individual MEDI9929 group and placebo group using the Fisher's exact test. A stratified log-rank test will be conducted to compare the time to first asthma control defined as a reduction from baseline in the mean ACQ-6 score ≥ 0.5 is first observed and the time to first partially control (0.75 < mean ACQ-6 score ≤ 1.5) and well controlled (mean ACQ-6 score of ≤ 0.75).

Asthma Daily Diary

Each item of the Asthma Daily Diary will be summarized showing change over time compared to baseline scores. Baseline will be defined as the 14-day period prior to dosing on Day 1 (ie, Day -15 to Day -1). Asthma Daily Diary data will be summarized as biweekly (14 day) means post dosing on Day 1. The change from baseline in the following endpoints will be analyzed:

- The mean symptom scores for daytime severity, daytime frequency, nighttime severity, and overall symptom score, where overall symptom score is the average of scores of daytime severity, daytime frequency, and nighttime severity
- The mean scores for the activity limitation questions
- Number of times rescue medication is used: daytime use, nighttime use, total rescue medication use (daytime + nighttime)
- The proportion of nights without nocturnal awakening and the proportion of nights without asthma-related nocturnal awakening (no awakening or wakening without rescue medication use)

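### The reason given for leaving the Japan/non-Japan stratum out of the primary model argues against an interaction, not against a main effect; the cost is a small loss of precision

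*Protocol*

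**What the plan says.** Section 4.6.1 makes region the first randomization factor: "Prior to randomization, subjects will be stratified by study site (non-Japanese and Japanese"), followed by eosinophil count and ICS dose level, giving eight strata. Sections 3.1.1 and 4.8.2 say the same.

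Section 4.8.3.1 specifies a negative binomial model with treatment, eosinophil category and ICS dose level. It then states that "the stratification factor of study sites (non-Japanese or Japanese) will not be included as a covariate for the primary analysis". The only reason offered is that the treatment effect is not expected to differ between Japanese and non-Japanese subjects. The Poisson sensitivity analysis is to consider the same covariates.

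The mixed model for continuous secondary endpoints in Section 4.8.1 also has no region term. Section 4.8.3.4 lists study site (non-Japanese versus Japanese) among the subgroup analyses that will be done, and among variables that may be added as covariates in a sensitivity analysis of the primary model.

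**The concern.** Two different terms are being confused. If the treatment effect is the same in both regions, no treatment-by-region interaction is needed. Whether a main effect is useful depends on whether subjects in Japan exacerbate at a different rate from subjects elsewhere on the same treatment. Two regions can share a rate ratio of 0.6 and still have very different placebo rates.

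If the background rates do differ, a model without region treats that difference as unexplained between-subject variation. The dispersion estimate rises, and the standard error of the treatment contrast rises with it, even though the design has balanced the arms on region. What is at stake is precision in the three primary comparisons, and a primary-analysis paragraph whose stated logic does not support its decision.

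**Working it through.** **Inputs from the protocol (Section 4.8.2).** Placebo rate 0.7 per year; 40% reduction, so 0.42 on active; 52 weeks; "a two-sided significance level of 0.1, 80% power, and a dispersion parameter of 0.7 based on the negative binomial distribution"; Japanese share about 15% of 552.

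**Input that must be assumed.** The Japan to non-Japan background rate ratio q is not given. It is varied from 1/3 to 2, with a common treatment effect.

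**Step 1: reproduce the plan's own figure.** The protocol states: "A total of 124 subjects per treatment group would be required to detect a 40% reduction in the annual AER".

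- Variance factor: 1/0.7 + 1/0.42 + 2 × 0.7 = 5.2095.
- n = (1.645 + 0.842)² × 5.2095 / ln(0.6)² = 123.4, so 124 per arm. Power at 124 is 80.2%.
- 124/0.9 gives 138 per arm, and 4 × 138 = 552.
- The detectable difference at 124 per arm is 27.7% to 28.6%, depending on the variance used, in line with the stated 28%.

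The plan's sample size is correct.

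**Step 2: dispersion due to region.** With a 15%/85% mix, the squared coefficient of variation of the background rate is

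CV² = 0.15 × 0.85 × (1 − q)² / (0.85 + 0.15q)².

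If 0.7 is the dispersion with region ignored, the dispersion within region satisfies (1 + k_adj)(1 + CV²) = 1.7, so k_adj = 1.7/(1 + CV²) − 1. The adjusted variance factor is 1/0.7 + 1/0.42 + 2k_adj, compared with 5.2095. Power is for 124 per arm.

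| q | CV² | k_adj | 0.7 − k_adj | Variance ratio | Power if adjusted |
|---|---|---|---|---|---|
| 1/3 | 0.070 | 0.589 | 0.11 | 0.957 | 81.7% |
| 0.5 | 0.037 | 0.639 | 0.06 | 0.977 | 81.0% |
| 0.7 | 0.013 | 0.679 | 0.02 | 0.992 | 80.4% |
| 1.5 | 0.028 | 0.654 | 0.05 | 0.982 | 80.8% |
| 2 | 0.096 | 0.551 | 0.15 | 0.943 | 82.2% |

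Against 80.2% unadjusted, the gain is about 0.2 to 2.0 points.

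**Step 3: simulation.** 2,000 trials per scenario, 124 per arm, 15% Japanese and balanced between arms, overall placebo rate 0.7. Here 0.7 is taken as the within-region dispersion, so the baseline differs slightly from Step 2. Both models were fitted to the same data. Monte Carlo error is about 0.9 points for power and 0.7 points for type I error. The eosinophil and ICS strata were not simulated.

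| q | Power, region omitted | Power, region included | Type I error, omitted | Type I error, included |
|---|---|---|---|---|
| 0.33 | 80.4% | 81.5% | 0.112 | 0.116 |
| 0.5 | 80.4% | 80.7% | 0.113 | 0.122 |
| 1 | 81.9% | 82.3% | 0.104 | 0.105 |
| 2 | 79.3% | 79.9% | 0.098 | 0.106 |
| 3 | 76.1% | 79.1% | 0.093 | 0.107 |

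The mean estimated rate ratio is about 0.60 with either model. At q = 2 the estimated dispersion is about 0.81 with region omitted and 0.67 with it included. At q = 3, outside the main range, the figures are 1.07 and 0.67.

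**Step 4: fewer Japanese subjects.** Sections 3.1.1 and 4.8.7 let non-Japanese sites fill the Stage I sample if Japan is slow. At an assumed 5% Japanese and q = 2: CV² = 0.05 × 0.95 × 1/1.05² = 0.043, k_adj = 0.630, variance ratio 5.069/5.2095 = 0.973, power 81.1%. The largest gain is then about one point.

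**The case against.** The best defence is that almost nothing is lost. The regional rates are assumed, there is no bias, and type I error is not made worse by omission. In the simulation the power gain for ratios of 0.33 to 2 is 0.3 to 1.1 points, against a Monte Carlo error of 0.9. A gain of about 0.4 points appears even at q = 1, where region explains nothing, so part of it may simply be a slightly higher rejection rate. Two of the three randomization factors are in the model, a regional subgroup analysis of the exacerbation rate is committed to, and a factor with about 21 Japanese subjects per arm (0.15 × 552/4 = 20.7), or fewer, could be left out for sparsity. All of this stands as to size. It does not rescue the stated reason: the protocol argues from equal treatment effects, not from sparsity or equal background rates. A subgroup analysis does not put region into the primary comparison, and the adjusted sensitivity analysis is only optional.

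A reader might also infer more than the text supports:

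- **That the time-to-first-exacerbation test is unstratified.** Section 4.8.3.2 says these times "will be analyzed as a supportive efficacy analysis for the primary objective using a log-rank test", while Section 4.8.4 says "A stratified log-rank test will be conducted to compare the time to first asthma control". The contrast is suggestive, but the first passage is silent rather than explicit and calls the analysis supportive. Log-rank strata and a hazard ratio are ordinary SAP content, and the SAP is not at hand.
- **That the model's eosinophil term would switch to a Day 1 value.** Section 4.8.1 says "Baseline value will be defined as the last valid assessment prior to the first administration of investigational product on Day 1", and Section 4.3.4 says "The Visit 3 (Week -1) blood eosinophil count from the local laboratory will be used for stratification". But the model uses the same 250 cells/μL cut as the strata, and Section 1.6.2 defines eosinophilic asthma from the local-laboratory screening count.
- **That subjects on medium-dose ICS plus maintenance oral corticosteroids would be analysed as medium.** Section 4.1.1 describes the ICS factor as including maintenance oral corticosteroids, and nothing in the protocol reclassifies these subjects.

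**Conclusion.** The point holds as a faulty rationale and a small, avoidable loss of precision in the primary model. It is not a validity problem: a reader might infer that leaving out a stratification factor biases the estimate or inflates the error rate, and the calculations show neither to a material degree. Under 15% Japanese subjects, a common treatment effect and a background rate ratio of 1/3 to 2, omission raises the dispersion by about 0.02 to 0.15. Adjusting reduces the variance of the log rate ratio by about 1% to 6%, or roughly 0 to 2 points of power. The effect vanishes as the ratio approaches 1, shrinks with a smaller Japanese share, and reaches about 3 points only at an assumed ratio of 3. The sample size of 124, inflated to 138 per arm, is unaffected. The change is worth making because it costs next to nothing, not because the analysis is unsound without it.

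**What to change.** In Section 4.8.3.1, add region (Japan or non-Japan) as a main effect to the negative binomial model, and delete the sentence that excludes it together with its reason. Make the same addition to the mixed model in Section 4.8.1; the gain there was not quantified. The Poisson sensitivity analysis then follows, since it takes the same covariates. No treatment-by-region interaction is needed in the primary model, and the regional subgroup analysis stays as planned.

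The cost is a wording change and one binary covariate (1 degree of freedom). Sample size, hypotheses and testing order do not change.

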4.8.3.2 Secondary Efficacy Analyses

Efficacy Outcomes in Pre-specified Subpopulations of Asthma

The primary endpoint of a reduction in the annualized AER measured at Week 52 and two other secondary endpoints of change from baseline in FEV_1 and in overall symptom score at Week 52 will be analyzed by the following pre-specified subpopulations of asthma:

1) eosinophilic and non-eosinophilic; 2) Th2 high/low (Corren et al, 2011); 3) FE_{NO} high/low; 4) periostin high/low; 5) current post-BD FEV₁ reversibility; and 6) allergic and non-allergic asthma.

Pulmonary Function

The effect of MEDI9929 on pulmonary function as measured by pre- and post-BD FEV_1 and FVC at the site, and PEFR at home will be assessed during the study. Change from baseline in the mean values and percent change from baseline at various time points will be summarized using descriptive statistics. Change from baseline in the mean values and percent change from baseline of FEV_1 and FVC at Week 52 will be analyzed.

Additional Analyses of Asthma Exacerbation

The analysis of exacerbations will also be conducted specifically for severe asthma exacerbations (hospitalizations). In addition, asthma exacerbations and severe asthma exacerbations through Week 64 will also be summarized.

Time to first asthma exacerbation and time to first severe asthma exacerbation will be analyzed as a supportive efficacy analysis for the primary objective using a log-rank test. Incidence of asthma exacerbations will also be evaluated by the proportion of subjects having one or more asthma exacerbations and one or more severe asthma exacerbations during the study.

Optimal Dose and Regimen

Dose response may be evaluated based on quadratic and linear negative binomial regression models to detect the dose response. The E_{max} model may be generated to determine the minimum effective dose. The details of the dose response analysis will be described in the SAP.

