2.2.2 Secondary Endpoints

- 1. Reduction in AER, change from baseline in FEV₁, and change from baseline in overall symptom score will be evaluated at Week 52 in the following pre-specified subpopulations of asthma: 1) eosinophilic and non-eosinophilic; 2) Th2 high/low 3) FE_{NO} high/low; 4) periostin high/low; 5) current post-BD FEV₁ reversibility; and 6) allergic and non-allergic.
- 2. Change from baseline in lung function as measured by pre-BD and post-BD FEV₁ and forced vital capacity (FVC) at Week 52 in the overall population.
- 3. Change from baseline in asthma symptoms (daytime and nighttime symptom frequency and severity, activity avoidance and limitation, asthma-related stress and fatigue as well as rescue asthma medication use) as measured by the Asthma Daily Diary, and other measures of asthma control as measured by the Asthma Control Questionnaire omitting FEV₁ (ACQ-6) at Week 52 in the overall population.
- 4. Annualized rate of hospitalizations due to asthma (ie, severe asthma exacerbations), time to first asthma exacerbation/severe asthma exacerbation, and proportion of subjects with one or more asthma exacerbations/severe asthma exacerbations at Week 52.
- 5. A dose- and exposure-response analysis will be done at Week 52 on reduction in AER, change from baseline in FEV₁, and change from baseline in overall symptom score to determine the optimal dose and regimen of MEDI9929.
- 6. Change from baseline in Asthma Quality of Life Questionnaire (Standardised; AQLQ[S])+12 and European Quality of Life 5 Dimensions 5 Level Version (EQ-5D-5L) at Week 52.
- 7. TEAEs, TESAEs, vital signs, laboratory assessments, and electrocardiogram (ECG) during the study (Week 0 [Day 1] to Week 64).
- 8. MEDI9929 PK and ADA during the study (Week 0 [Day 1] to Week 64).

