treatment group to accommodate a 10% loss of information due to dropouts. The minimal detectable difference is approximately 28% reduction in annual AER. Figure 4.8.2-1 provides power calculations based on varying sample sizes for a selected treatment effect of AER reduction of 40% and 50%. The minimum acceptable reduction in the annual AER of 40% for the study population was based upon an expected reduction of approximately 50% in a Th2-driven asthma population which appears to be achievable in competitors which target Th2 cytokines (eg, IL-13, IL-5) and a more modest reduction in a non-Th2 asthma population for which there are little data and no current competitors.

[figure not shown]

Figure 4.8.2-1 Power Calculations for an Annual Asthma Exacerbation Rate of 40 Percent or 50 Percent

AER = asthma exacerbation rate; AERR =asthma exacerbation rate reduction; yr = year Note: The sample sizes do not reflect the projected dropout rate.

It is generally recommended that Japanese subjects be included in studies to identify interethnic differences in the dose-response relationship early in clinical development. The target percentage of Japanese subjects for inclusion in this study is approximately 15% of the targeted enrollment of 552 subjects. A subgroup analysis of the non-Japanese subjects and Japanese subjects will be performed. Due to a small sample size, the subgroup analysis of the

Japanese subjects will not have sufficient power to detect differences with statistical significance.

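### The dose-response analysis promised by secondary endpoint 5 is only optional in Section 4.8.3.2, and the linear and quadratic models named for detection fit a flat response poorly on most dose scales

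*Protocol*

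**What the plan says.** Secondary objective 5 (Section 2.1.2) is to find the dose and regimen for later studies. The matching endpoint 5 in Section 2.2.2 is firm: "A dose- and exposure-response analysis will be done at Week 52 on reduction in AER", and it also covers change from baseline in FEV1 and in overall symptom score.

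The method is in Section 4.8.3.2 under Optimal Dose and Regimen: "Dose response may be evaluated based on quadratic and linear negative binomial regression models to detect the dose response". The next sentence names an Emax model, also as a possibility, for finding the minimum effective dose. The last leaves details to the SAP. Section 4.8.6 treats the exposure-response side as optional too.

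The only effect size given by dose is in Section 4.8.2, where the trial is sized "to detect a 40% reduction in the annual AER for each MEDI9929 dose group compared to placebo group". The same section describes this as "The minimum acceptable reduction in the annual AER of 40% for the study population".

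**The concern.** There are two points.

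1. **Commitment.** The endpoint says the analysis *will* happen and the analysis section says it *may*. The models named for detection are count models, so they serve AER but not FEV1 or symptom score. An SAP that followed Section 4.8.3.2 to the letter could leave out what endpoint 5 promises.

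2. **Shape.** The protocol did not leave the detection shapes wholly to the SAP; it named them. Because 280 mg every 2 weeks is 560 mg per 4 weeks, the three active regimens span 560/70 = 8-fold. If most of the effect is already present at the low dose, a straight line in mg cannot follow it, and a quadratic has to rise and bend back. A reader using these fits to inform dose choice could undervalue the low dose (from the line) or infer an intermediate best dose (from the quadratic).

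The primary analysis is not affected. What is at stake is objective 5.

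**Working it through.** **Inputs (Section 4.8.2).** Placebo rate: "assuming an AER of 0.7 in the placebo group". Active rate 0.7 × 0.6 = 0.42. Also "a two-sided significance level of 0.1, 80% power, and a dispersion parameter of 0.7". Follow-up is 1 year.

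**The plan's own figure.** n = (1.645 + 0.842)² × [(1/0.7 + 0.7) + (1/0.42 + 0.7)] / (ln 0.6)² = 6.183 × 5.210 / 0.2609 = 123.4, which matches "A total of 124 subjects per treatment group would be required". Then 124/0.9 = 137.8, so 138 per arm and 4 × 138 = 552. The sample size reproduces and is not in dispute.

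**Test scenario (an assumption).** Rates 0.70/0.42/0.42/0.42, that is, 40% at every dose. Each arm's log rate has variance (1/rate + 0.7)/124. The dose-response models are fitted to the four log rates by weighted least squares.

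**Fits on mg per 4 weeks, with x = dose/560 = 0, 0.125, 0.375, 1.**

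- Linear: slope −0.383. Reductions are 1 − exp(−0.383x) = 4.7%, 13.4% and 31.8% at low, middle and high dose. Slope divided by its standard error is 1.96, so power at two-sided 0.1 is Φ(1.96 − 1.645) ≈ 62%. A single pairwise test has 80%.
- Quadratic: log rate ratio −1.984x + 1.566x². Reductions are 20.0%, 40.8% and 34.2%. The turning point is at x = 1.984/(2 × 1.566) = 0.633, about 355 mg per 4 weeks, with a fitted reduction of 46.7%. In 20,000 simulated sets of arm estimates, the fitted peak lay inside the dose range in 93% (124 per arm) to 94% (138 per arm).

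A maximum-likelihood negative binomial fit to the same rates gives 4.6/13.1/31.2% (linear) and 20.1/40.9/33.9% with a peak at 353 mg (quadratic).

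**Other dose axes.** The protocol does not fix one. The truth is 40/40/40% throughout, with 124 per arm and two-sided 0.1.

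| Axis | Linear fit (%) | Linear power | Quadratic fit (%) | Joint 2-df power |
|---|---|---|---|---|
| mg per 4 weeks | 5 / 13 / 32 | 62% | 20 / 41 / 34 | 80% |
| labelled mg (70/210/280) | 11 / 29 / 37 | 80% | 31 / 44 / 34 (peak 182) | 86% |
| ordinal | 16 / 29 / 40 | 83% | 34 / 44 / 37 | 88% |
| log(1 + mg per 4 weeks) | 32 / 38 / 43 | 93% | 39.5 / 40.8 / 39.6 | 89% |

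**Less extreme truths (mg per 4 weeks).** With true reductions of 29/40/40%, the linear fit gives 5/15/35% and the quadratic 20/40/37%, peaking at 370 mg. With 20/36/40%, the linear fit gives 6/16/38%. The quadratic is then close at the studied doses (17/36/39%) but still peaks inside the range, near 407 mg.

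**Alternatives on the plateau.**

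- Emax reproduces 40/40/40%, but only as ED50 goes to 0, so it cannot locate a minimum effective dose below 70 mg.
- A multiple-contrast test (linear; Emax with ED50 35 and 210; log(1 + d/20); one-sided 0.05, critical value about 1.88) has 88% to 90% power, depending on how the contrasts are weighted.
- If the truth is exactly linear, the multiple-contrast test has 81% to 82%, against 84% for the linear test alone and 76% for the joint 2-df test.

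**The case against.** Four readings go further than the documents allow.

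- **That the plan predicts a plateau.** It does not. The 40% per dose is a pairwise power assumption and a minimum acceptable effect. Section 3.2.1 explains the doses by limited exposure overlap and the lack of an established pharmacodynamic marker, so the shape was treated as unknown. The plateau is a fair test case and no more.
- **That a dose will be read off the line or the quadratic.** Section 4.8.3.2 names these models to detect a response and names Emax, which can follow a plateau, for the minimum effective dose. Nothing says the turning point selects a dose.
- **That the named pair would often miss the response.** The 62% belongs to the linear trend alone on one axis. The joint test has 80% there and 86% to 89% on the others.
- **That the low dose would be judged inactive.** The understatement is worst for the line on mg per 4 weeks, while the false peak belongs only to the quadratic. Section 4.8.3.1 compares each dose with placebo directly, so the low-dose effect would be visible whatever a trend model shows.

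It is also fair that the dose axis and the FEV1 and symptom-score models are details a protocol may leave to the SAP. And *may* could be read as leaving the method open rather than the analysis.

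What stands is that the text as written does not bind the sponsor to what endpoint 5 promises. The detection shapes it names also distort a flat response on the mg and ordinal axes.

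**Conclusion.** The point holds in a limited form. A firm endpoint on three outcomes is backed by optional text, with count models for detection and an optional Emax model for one purpose. If the doses have similar effects and the axis is total mg per 4 weeks, the linear fit shows about 5% at the low dose against a true 40%, with about 62% power. The quadratic suggests a peak near 355 mg that does not exist. The distortion shrinks on labelled or ordinal dose and is nearly gone for the quadratic on log dose. These figures rest on the plan's rate and dispersion, 124 per arm, and an assumed plateau.

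This is worth correcting because a stated objective depends on it. It is not a threat to the primary analysis.

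**What to change.** 1. Make Section 4.8.3.2 agree with endpoint 5: state that the dose-response analysis *will* be done for AER, FEV1 and overall symptom score, and align the exposure-response wording in Section 4.8.6.
2. State the dose axis, for example total mg per 4 weeks (0/70/210/560).
3. Make a plateau-capable analysis primary for dose-response. This can be the Emax model already named, or a multiple-contrast test (MCP-Mod) with linear, log-linear and Emax shapes applied to the model-based arm estimates (log rate ratios for AER).
4. Keep the linear and quadratic fits as supportive trend checks, and state that no optimal dose is taken from the quadratic.

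The cost is wording and programming, with no new data. With the multiple-contrast test, about 2 to 3 points of power are lost if the truth is exactly linear, and the candidate set assumes a monotone response, which the protocol does not currently assume.
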